2.2 Safety Analysis Set

The safety analysis set will include all eyes with attempted use of the UNITY VCS (successful or aborted after contact with the eye) and will be used for the safety outcomes. Attempted use of the UNITY VCS is defined as any time the device makes contact with the eye.

3 SUBJECT CHARACTERISTICS AND STUDY CONDUCT SUMMARIES

Subject characteristics and study conduct summaries will include subject disposition, demographics, and reason for surgery. Summaries will be presented for subjects in the safety and full analysis sets indicating the count receiving posterior segment (i.e., vitreoretinal) only or a combined (i.e., vitreoretinal and simultaneous cataract) procedure. Additionally, procedures will be summarized by simple and complex. Listings will be provided for medical history, screen failures by reason, protocol deviations, baseline medications, and for subjects included in the safety analysis set but excluded from the full analysis set. All descriptive summary statistics will be displayed with count and percent for categorical data such as sex, age, race, and ethnicity. Count (n), mean, standard deviation, median, minimum, and maximum will be presented for continuous variables such as age.

Subject characteristics and study conduct summaries will be presented for the full analysis set unless the safety analysis set is different, in which case they will be presented for both.

4 EFFECTIVENESS ANALYSIS STRATEGY

4.1 Effectiveness Endpoints

Primary Endpoint

The primary performance endpoint is the percentage of surgeons reporting ‘yes’ to the binary question of: ***“Did UNITY VCS using vitreoretinal or combined surgical functionality perform per the intended use as defined in protocol Section 5.1?”***

Secondary Endpoints

- Total time in the eye from first entry into eye/first trocar in, to incision closure/last trocar out
- Achievement of anatomical success at 3 months postop, i.e., percent of ‘yes’ responses to the question “Was anatomical success achieved for intended treatment (e.g., macular hole closure, retinal attachment, etc. as applicable for the patient’s condition)?”
- Change in BCDVA at 3 months postop when compared to preop

4.2 Effectiveness Hypotheses

No hypothesis testing will be performed. Analyses will be descriptive only.

4.3 Statistical Methods for Effectiveness Analyses

Standard descriptive statistics will be presented based on the type. Individual subject data listings will also be provided. No imputation of missing data is planned. The full analysis set will be used for all effectiveness analysis and all analyses will be based on the study eye unless otherwise stated.

4.3.1 Analysis of the Primary Endpoint

After each surgery, the surgeon completes a user questionnaire. For subjects in the full analysis set, the rate of ‘yes’ responses to the question ***“Did UNITY VCS using vitreoretinal or combined surgical functionality perform per the intended use as defined in protocol Section 5.1?”*** will be presented with a count and percentage and will be accompanied by a two-sided exact binomial 95% confidence interval.

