## **8 STUDY POPULATION**

The study population will consist of male and female subjects (18 years or older) requiring posterior segment surgery in the operating room with or without simultaneous cataract surgery (unilaterally). It is aimed to enroll (consent) approximately 120 subjects in up to 8 sites in AUS and/or the USA with a target of 100 subjects treated, with approximately 10 to 40 subjects per

site. Site-specific targets may vary based upon individual site capabilities and each site may include more than one surgeon. Estimated time needed to recruit subjects for the study is approximately 3 months; however, unanticipated circumstances may shorten or lengthen this time and would not require amendment of this protocol. Because a 10% screening failure rate is expected and 10% for loss to follow-up, approximately 120 subjects are expected to be enrolled to ensure 100 completed subjects.

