## **10.2 Description of Study Procedures and Assessments**

Study-specific procedures and assessments described here may include standard of care; other standard of care procedures performed in the clinical management of the subject are not excluded.

Detailed descriptions of assessments and procedures are provided in the MOP. The investigator is responsible for ensuring responsibilities for all procedures and assessments are delegated to appropriately qualified site personnel.

The enrollment on this study is competitive and once the target number of subjects is achieved, sponsor will close the enrollment.

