7 SAMPLE SIZE AND POWER CALCULATIONS

Based on a sample of 100 surgeries, the expected half-width of the 95% confidence interval for the percentage of surgeons reporting 'yes' to the question "***Did UNITY VCS using vitreoretinal or combined surgical functionality perform per the intended use as defined in protocol Section 5.1?***" will be $1.96\sqrt{p(1-p)/100}$. This half-width is widest at $p = 50\%$. Under this conservative assumption, the expected half-width is < 10% given the sample size of 100.

Allow enrollment for an additional 10% for screen failure and 10% for loss to follow-up to ensure 100 completed subjects.

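### The exact binomial interval and the stated precision for the primary 'yes' rate assume independent surgeries, and will overstate precision if answers correlate within surgeon

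*SAP*

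**What the plan says.** - **Unit of response.** SAP 4.3.1 (and Protocol 12.4.1.2): "After each surgery, the surgeon completes a user questionnaire". The full analysis set consists of eyes, so there is one answer per eye operated on.
- **Interval.** The same sections pool these answers into one rate, which "will be presented with a count and percentage and will be accompanied by a two-sided exact binomial 95% confidence interval".
- **Endpoint label.** SAP 4.1 (and Protocol 12.4.1): "The primary performance endpoint is the percentage of surgeons reporting" 'yes'. The Protocol summary and Table 6-1 instead define it as a percentage of responses.
- **Precision.** SAP 7 (and Protocol 12.8): "Based on a sample of 100 surgeries, the expected half-width of the 95% confidence interval" follows from the variance p(1-p)/100, and at p = 50% "the expected half-width is < 10% given the sample size of 100".
- **Who answers.** Protocol 8 plans up to 8 sites with about 10 to 40 subjects per site, and adds that "each site may include more than one surgeon". The total number of surgeons is not given. Protocol 10.2 says "The enrollment on this study is competitive and once the target number of subjects is achieved", the sponsor closes recruitment.
- **What is not visible.** The public text has no design effect, no clustering adjustment and no summary of this endpoint by surgeon or site. SAP 3 breaks procedures down by type and by complexity, not by operator.

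**The concern.** An exact binomial interval needs independent answers. Here the same surgeon gives a judgement on the same system many times. A personal threshold for saying 'yes', surgical skill and learning on a new console are all shared between one surgeon's cases, so some correlation is plausible. Positive correlation means that 100 answers carry less information than 100 independent ones.

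The study is descriptive, so this interval is the only statement of uncertainty on the primary result. That result is meant to support marketing in Europe, and Protocol 7.2 intends the results to be compared with external evidence. A pooled rate also cannot separate a uniform 92% from near-unanimous approval by a main enroller and much lower approval by another surgeon.

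**Working it through.** **Inputs from the documents:** n = 100 surgeries (SAP 7); up to 8 sites, about 10 to 40 subjects each (Protocol 8). Since 100/40 = 2.5, three sites could supply the whole sample.

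**Assumptions (not in the documents):** intraclass correlation (ICC) within surgeon, number of surgeons, split of cases between them, and true 'yes' rate. Ranges are shown for each.

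**1. The plan's own figure.** 1.96 × √(0.5 × 0.5/100) = 9.8 points, so the stated bound is reproduced. This is the Wald formula. The exact interval that the SAP will report runs from 39.8% to 60.2% at 50/100, a half-width of 10.2 points, so it just misses the bound even with independent answers.

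**2. Half-width with clustering.** Design effect DE = 1 + (m − 1) × ICC with m = 100/k for k equal raters. Half-width at p = 50% is 9.8 × √DE, and the effective n is 100/DE. Example: k = 8, m = 12.5, ICC 0.05 gives DE = 1 + 11.5 × 0.05 = 1.575, half-width 9.8 × 1.255 = 12.3, effective n = 63.

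| Raters (equal) | ICC 0.01 | 0.05 | 0.10 | 0.20 |
|---|---|---|---|---|
| 16 | 10.1 | 11.0 | 12.1 | 14.0 |
| 8 | 10.3 | 12.3 | 14.4 | 17.8 |
| 3 | 11.3 | 15.9 | 20.2 | 26.8 |

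With 8 raters the Wald half-width passes 10 points once DE exceeds (10/9.8)² = 1.041, that is at ICC = 0.041/11.5, about 0.004.

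**3. Coverage of the planned exact 95% interval.** Beta-binomial simulation, 100,000 runs per cell, 100 surgeries in total (percent, rounded):

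| Raters | True rate | ICC 0 | 0.02 | 0.05 | 0.10 | 0.20 |
|---|---|---|---|---|---|---|
| 8 (12 or 13 each) | 90% | 96 | 93 | 89 | 83 | 72 |
| 8 | 95% | 98 | 97 | 94 | 90 | 82 |
| Four (40/30/20/10) | 90% | 96 | 89 | 80 | 69 | 54 |
| Four (40/30/20/10) | 95% | 98 | 94 | 89 | 80 | 66 |
| 16 (6 or 7 each) | 90% | 96 | 94 | 93 | 90 | 84 |
| 16 | 95% | 98 | 98 | 97 | 95 | 91 |
| 16 | 98% | 98 | 98 | 97 | 96 | 93 |

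The loss is material with 8 or fewer raters and moderate correlation. It largely disappears with more raters and a high 'yes' rate, because the exact interval is conservative there.

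**4. Would a clustered interval do better?** This depends on how it is specified. In the Korn-Graubard interval the effective n is p̂(1 − p̂)/v, where v is the between-surgeon variance estimate. It is multiplied by (t with n − 1 df / t with k − 1 df)² at the 97.5% point and capped at n; Clopper-Pearson limits are then taken on that effective n. At a true rate of 90% and ICC 0.05/0.1/0.2:

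- Full method: 96/95/93% with 8 raters; 97/95/92% with four unequal raters.
- Without the t adjustment and the cap: 84/83/79% with four unequal raters.
- Without the cap, with 8 raters and truly independent answers: the estimated effective n exceeds 100 in nearly 60% of runs.
- Full method, four unequal raters, true rate 95%: 95/90/80%. It is better than the planned interval but still short at high ICC.

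**The case against.** The strongest reply is that the problem is conditional. The documents give no ICC, no expected 'yes' rate and no number of surgeons, and Protocol 8 allows several surgeons per site, so 8 is a limit on sites and not on raters. The full analysis set holds only successfully completed surgeries, so a high rate is plausible, and the table shows settings in which the planned interval performs as labelled. This stands. A reader might infer that the interval is certainly too narrow; the documents do not support that.

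A reader might also infer that differences between operators will stay hidden. That goes too far. SAP 4.3 plans individual subject listings, and SAP 4.4 and 6 are absent from the public copy, so a breakdown by surgeon or site cannot be ruled out. Still, a listing is not a summary, and no visible text says that it will identify the surgeon.

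Third, the analysis is descriptive, with no test or threshold, so no pass/fail decision turns on the width. This limits the consequence to overstated precision, but it does not remove it.

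Fourth, the reference to a percentage of surgeons is loose wording and not an open question: the Protocol summary, Table 6-1 and the analysis sections all fix the unit as one response per surgery. I agree; it needs an edit, not a new endpoint.

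**Conclusion.** The concern holds in conditional form. SAP 4.3.1 and SAP 7, with Protocol 12.4.1.2 and 12.8, rest on independent surgeries, while the design has surgeons rating the same device repeatedly. If answers correlate within surgeon, the interval will be too narrow. At a true rate of 90% and ICC 0.05 to 0.2, nominal 95% coverage drops to about 89–72% with 8 raters and 80–54% with four unequal raters. With about 16 raters and a rate of 95% or more it remains about 95% or higher up to ICC 0.1. All of these rest on assumed correlations, rater numbers and true rates.

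Separately, and without any assumption about correlation, the half-width bound of 10 points is met by the Wald formula (9.8) but not by the planned exact interval at 50/100 (10.2).

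The evidence supports adding information beside the planned interval. It does not support replacing that interval, because the clustered alternative is itself unreliable with very few surgeons and a high 'yes' rate.

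**What to change.** 1. **SAP 4.3.1 and Protocol 12.4.1.2:** report the number of surgeons and one table of 'yes' counts over surgeries, by surgeon within site. This is the most useful step, since the ICC can hardly be estimated if almost every answer is 'yes'.
2. **Same sections:** keep the exact binomial interval and add a surgeon-clustered supporting interval, specified in full before database lock: Korn-Graubard, that is Clopper-Pearson on the effective sample size, surgeon as cluster, with the t degrees-of-freedom adjustment and the effective n capped at the actual n. If all answers are 'yes', report the simple exact interval and state that it assumes independence.
3. **SAP 7 and Protocol 12.8:** say that the half-width at p = 50% is 9.8 points by the Wald formula and 10.2 for the planned exact interval at 50/100, and that both hold only for independent surgeries.
4. **SAP 4.1 and 7, Protocol 12.4.1 and 12.8:** call the endpoint the percentage of surgeries with a 'yes', to match the analysis.

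**Cost:** wording, one table and one extra interval, which will usually be wider and is less reliable with very few surgeons. Surgeon identity should be recoverable, since Protocol 13.2 requires authors of source entries to be identifiable. The questionnaire form is not shown, so confirm that it records the surgeon.

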4.3.2 Analysis of the Secondary Endpoints

4.3.2.1 Total Time in Eye

Total time in the eye from first entry into eye/first trocar in, to incision closure/last trocar out will be evaluated. At the surgical visit, the total time in the eye will be recorded as the time from first entry into eye/first trocar in, to incision closure/last trocar out. The total time in eye will be summarized with the number of observations, mean, standard deviation, median, minimum, and maximum times in minute. A 95% confidence interval for the mean based on the t-distribution will be presented. Additionally, a 95% non-parametric confidence interval for the median will be constructed. A listing will accompany this summary.

4.3.2.2 Achievement of Anatomical Success

Achievement of anatomical success at 3 months postop, i.e., percent of ‘yes’ responses to the question “Was anatomical success achieved for intended treatment (e.g., macular hole closure, retinal attachment, etc. as applicable for the patient’s condition)?” will be summarized. At the end of follow-up for each patient, surgeons will evaluate the success of the surgery. For subjects in the full analysis set, the rate of ‘yes’ responses will be presented with a count and percentage and will be accompanied by a two-sided exact binomial 95% confidence interval.

4.3.2.3 Change in BCDVA

Change in BCDVA at 3 months postop when compared to preop will be calculated. BCDVA will be recorded in Snellen and collected at screening, 1 month, and 3 months. Results will be converted to decimal VA. Observed decimal BCDVA values at each study visit and change from 3 months postoperative visit to screening value for the study eye will be presented descriptively (count, mean, median, standard deviation, minimum, maximum, and a 95% confidence interval for the mean based on the t-distribution). A categorical summary of Snellen values (not converted to decimal VA) will be produced and will include counts and percentages for each category at screening, 1 month, and 3 months. A listing will be provided which presents visual acuity results at each visit, including data from 1 day and 1 week visits, where uncorrected data may be recorded per standard of care.

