## 8.1 Inclusion Criteria

Written informed consent must be obtained before any study specific assessment is performed. Upon signing informed consent, the subject is considered enrolled in the study.

Subjects eligible for inclusion in this study must fulfill **all** of the following criteria:

1. Subject must be able to understand and sign an IRB/IEC approved informed consent form.
2. Willing and able to attend all scheduled study visits as required per protocol.
3. Adults  $\geq$  18 years requiring posterior segment surgery in the operating room without or with simultaneous cataract surgery
4. Clear media except for cataract and vitreous hemorrhage
5. In simultaneous cataract and vitreoretinal surgery, eligible to undergo primary hydrophobic acrylic IOL implantation into the capsular bag
6. For those with planned simultaneous cataract and vitreoretinal surgery, keratometry of 41 to 46 D
7. For those with planned simultaneous cataract and vitreoretinal surgery, with following biometry, anterior chamber depth of greater than 2.5 mm, and axial length of 22 to 28 mm

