# **12 ANALYSIS PLAN**

## **12.1 Subject Evaluability**

Final subject evaluability must be determined prior to locking the database, based upon the deviations and evaluability plan.

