### 12.4.2.2 Analysis Methods

At the surgical visit, the total time in the eye will be recorded as the time from first entry into eye/first trocar in, to incision closure/last trocar out. The total time in eye will be summarized with the number of observations, mean, standard deviation, median, minimum, and maximum times in minutes. A listing will accompany this summary.

At the end of follow-up for each patient, surgeons will evaluate the success of the surgery. For subjects in the full analysis set, the rate of ‘yes’ responses to the question “was anatomical success achieved for intended treatment (e.g., macular hole closure, retinal attachment, etc. as applicable for the patient’s condition)?” will be presented with a count and percentage and will be accompanied by a two-sided exact binomial 95% confidence interval.

BCDVA will be recorded in Snellen and collected at screening, 1 month, and 3 months. BCDVA will be converted to decimal VA. Observed decimal BCDVA values at each study visit and change from 3 months postoperative visit to screening value for the study eye will be presented descriptively (count, mean, median, standard deviation, minimum, and maximum). A categorical summary of Snellen values (not converted to decimal VA) will be produced and will include counts and percentages for each category at screening, 1 month, and 3 months. A listing will be provided which presents visual acuity results at each visit, including data from 1 day and 1 week visits, where uncorrected data may be recorded per standard of care.

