10 APPENDIX

Table 10-1 Schedule of Study Procedures and Assessments

	Nominal Time ± Window Limits							Early Exit ³	Unscheduled Visit ³
	Visit 0 (Screening)	Visit 00 (Operative)	Visit 1 (1 Day)	Visit 2 (1 week)	Visit 3 (1 month)	Visit 4/Exit (3 month)			
Procedure/ Assessment	Day -30 to 0	Day 0	Day 1 + 2 Days	Day 7 ± 3 Days	Day 30 ± 14 Days	Day 90 ± 14 Days	N/A	N/A	
Eye	Both eyes	Study eye	Study eye	Study eye	Study eye	Study eye	Study eye	Study eye	Study eye
Informed Consent	X								
Demographics	X								
Medical History	X								
Concomitant Medications	X	X	X	X	X	X	X	X	
Inclusion/Exclusion	X								
Urine Pregnancy Test ²	X								
Dilated Pupil Size	X								
Keratometry*	X								
Biometry (ACD, AL)*	X								
Slit lamp exam	X		X	X	X	X	X	X	
Monocular BCDVA Using Snellen chart ^c	X		X ^a	X ^a	X	X	X	X	
IOP	X		X	X	X	X	X	X	

	Nominal Time ± Window Limits							Early Exit ³	Unscheduled Visit ³
	Visit 0 (Screening)	Visit 00 ² (Operative)	Visit 1 (1 Day)	Visit 2 (1 week)	Visit 3 (1 month)	Visit 4/Exit (3 month)			
Procedure/ Assessment	Day -30 to 0	Day 0	Day 1 + 2 Days	Day 7 ± 3 Days	Day 30 ± 14 Days	Day 90 ± 14 Days	N/A	N/A	
Eye	Both eyes	Study eye	Study eye	Study eye	Study eye	Study eye	Study eye	Study eye	
Dilated Fundus Exam	X		X ^b	X	X	X	X	X	
Total time in eye		X							
User Questionnaire		X							
Adverse Events	X	X	X	X	X	X	X	X	X
Device Deficiencies		X							

² Women of child-bearing potential only

³ Unscheduled/Early Exit Visit – additional study assessments may be performed per investigator's discretion

^a Visual acuity (VA) to be conducted per site's standard of care using Snellen chart

^b Optional, to be performed per site's standard of care as needed

^c BCDVA is done using manifest refraction

*As applicable

Table 10-2

Conversion of Snellen in Feet to Snellen in Meters

Distance	
Snellen Feet 20/	Equivalent Meter 6/
10	3.0
12.5	3.8
16	4.8
20	6.0
25	7.5
30	9.0
32	9.6
40	12.0
50	15.0
60	18.0
63	18.9
70	21.0
80	24.0
100	30.0
114	34.2
125	37.5
150	45.0
160	48.0
200	60.0

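### BCDVA change is averaged only on the decimal scale, where equal acuity ratios count unequally; adding a logMAR mean, SD and 95% CI in the SAP would be a cheap improvement

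*SAP*

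**What the plan says.** SAP 4.3.2.3 has BCDVA recorded in Snellen at screening, 1 month and 3 months and then converted to decimal acuity. The summary covers "Observed decimal BCDVA values at each study visit and change from 3 months postoperative visit to screening value for the study eye": count, mean, median, SD, minimum, maximum and "a 95% confidence interval for the mean based on the t-distribution". Protocol 12.4.2.2 uses the same scale and the same statistics, but without the interval. Neither passage mentions logMAR or gives a reason for the decimal scale.

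The SAP also plans Snellen categories by visit and a listing of acuity at every visit. No test is planned for any endpoint (SAP 4.2), and the sample size rests on the primary endpoint alone (SAP 7).

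On the range of acuity, Protocol 8.1 requires "Clear media except for cataract and vitreous hemorrhage", and neither 8.1 nor 8.2 sets an acuity limit. Protocol 5.1 describes surgery for conditions that run from floaters to retinal detachment.

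The only acuity table in the SAP appendix is headed "Conversion of Snellen in Feet to Snellen in Meters". It runs from 20/10 to 20/200.

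**The concern.** An arithmetic mean of decimal acuity treats a fixed decimal difference as the same amount of change anywhere on the chart. A fixed decimal difference is a large proportional change in a poor eye and a small one in a good eye. In a trial open to eyes across a wide range of acuity, the mean change therefore mixes two things: the ratio by which eyes improved, and where they started.

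This is one of three secondary performance endpoints and the only one based on visual function. The interval around the decimal mean is the only interval the supplied text gives for it. The SAP gives time in the eye a non-parametric interval for the median (4.3.2.1), but BCDVA gets none. What is at stake is how the size of the reported change is read, not any formal decision.

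**Working it through.** **Inputs.** For a Snellen value 20/x, decimal acuity is 20/x and logMAR is −log10(decimal) = log10(x/20). The acuities used are rows of SAP Table 10-2. Feet or meters makes no difference: 20/200 and 6/60.0 are both 0.10.

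**The plan's own figure.** None is given for BCDVA. The only precision figure, for the primary endpoint, reproduces: 1.96 × √(0.5 × 0.5/100) = 0.098, below 10% as stated. It does not bear on this point.

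**Step 1: the same doubling at two places.**
- 20/200 to 20/100: decimal 0.20 − 0.10 = +0.10; logMAR −0.301.
- 20/40 to 20/20: decimal 1.00 − 0.50 = +0.50; logMAR −0.301.
- Ratio of decimal weights: 0.50/0.10 = 5.

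**Step 2: one 1.25-fold step between adjacent rows of Table 10-2.**
- 20/200 to 20/160: decimal 0.125 − 0.100 = +0.025; logMAR −0.097.
- 20/25 to 20/20: decimal 1.00 − 0.80 = +0.20; logMAR −0.097.
- Ratio of decimal weights: 0.20/0.025 = 8.

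**Step 3: effect on a mean.** The documents give no acuity distribution, so both mixes are assumed. In each, 20% of eyes go from 20/20 to 20/25 (decimal −0.20, logMAR +0.0969) and 80% start at 20/200 and gain.
- Gainers reach 20/100. Decimal mean: 0.8 × 0.10 − 0.2 × 0.20 = +0.040, which is 40% of the gainers' own change. LogMAR mean: 0.8 × (−0.301) + 0.2 × 0.0969 = −0.221, which is 74%.
- Gainers reach 20/40. Decimal mean: 0.8 × 0.40 − 0.2 × 0.20 = +0.280, or 70%. LogMAR mean: 0.8 × (−0.699) + 0.2 × 0.0969 = −0.540, or 77%.

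So the scales can differ clearly or hardly at all, depending on the mix.

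**Step 4: sensitivity to acuity that is not a Snellen fraction.** Assume k of 90 eyes have such a value at one visit, and the decimal value assigned moves from 0.005 (logMAR 2.301) to 0.02 (logMAR 1.699).
- Shift in the logMAR mean: k × (2.301 − 1.699)/90 = 0.013 for k = 2, 0.033 for k = 5 and 0.054 for k = 8.
- Shift in the decimal mean for k = 5: 5 × 0.015/90 = 0.0008.

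**The case against.** The strongest reply is that this is a choice of scale, not an error. Decimal acuity is pre-specified, the two documents agree, nothing is tested, and neither document says that equal ratios should count equally. All of that stands, and it is why the point is optional.

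The second reply is that the median, range, Snellen categories and listing already protect the reader, and that anyone with the listing can compute logMAR for the fractions. This stands in part. The category table is by visit and does not show change within an eye, and the median change has no interval.

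The third reply is that logMAR brings its own weakness. Vitreous hemorrhage is allowed, so acuity that cannot be written as a fraction is plausible, and Step 4 shows that the logMAR mean moves far more with the value assigned. With a larger assumed share, 20 of 100 eyes moved from 1.6 to 2.7 logMAR, the screening mean shifts by 0.22 logMAR against 0.005 decimal. This stands, and it is a reason to add logMAR rather than replace the decimal summary.

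A reader might also infer stronger points that the documents do not support:
- That the decimal mean would show a loss where logMAR shows a gain. This is possible by construction: 50 eyes from 20/200 to 20/50 and 50 from 20/20 to 20/40 give −0.100 decimal (a loss) and −0.151 logMAR (a gain). That mix has half the eyes starting at 20/20 and worsening, and nothing in the documents suggests it.
- That gains in poor eyes are ignored. They are not: 20/200 to 20/40 is +0.40. The weighting is uneven, not absent.
- That logMAR would compare better with outside results. Protocol 7.2 foresees such a comparison but names no scale.
- That a rule for non-fraction acuity is missing. Protocol 10.2 says "Detailed descriptions of assessments and procedures are provided in the MOP", and Protocol 12.1 says "Final subject evaluability must be determined prior to locking the database, based upon the deviations and evaluability plan". Neither document was available, and the public SAP text does not include sections 4.4 and 6.
- That the change will be computed backwards. "change from 3 months postoperative visit to screening value for the study eye will be presented descriptively" read literally reverses the endpoint, but SAP 4.3.2.3 opens with "Change in BCDVA at 3 months postop when compared to preop will be calculated", so the intent is clear and this is a wording slip.

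**Conclusion.** The point holds as a low-impact improvement. On the decimal scale equal acuity ratios are weighted 5-fold differently for a doubling (20/200 against 20/40) and 8-fold for one 1.25-fold step in Table 10-2. With no acuity limit in eligibility, the reported mean and its interval depend on starting acuity as well as on the ratio gained.

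The weights are exact arithmetic. The effect on a mean in Step 3 rests on assumed mixes, and how far the two scales would differ in this trial cannot be established from the documents. The value of a logMAR summary rests on the premise that a ratio of acuity is a sensible unit of change, which the plan neither adopts nor rejects. No test, success criterion or sample size is affected.

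**What to change.** Change SAP 4.3.2.3 only:
- Keep the decimal summary, the Snellen categories and the listing as they are.
- Add the mean, SD and t-based 95% CI of logMAR BCDVA (−log10 of decimal) at screening, 1 month and 3 months, and of the change.
- Define change as 3-month minus screening, and state that a negative logMAR change is improvement. Using the same subtraction for the decimal change also settles the wording slip.
- Report at each of these visits the number of eyes whose acuity was not recorded as a Snellen fraction and the value used for them, by reference if the rule sits in another study document. Repeat the logMAR summary under one alternative value.

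The cost is a short SAP addition and a few lines of programming on data already collected. The protocol's own summaries are unchanged, so Protocol 12.4.2.2 need not be edited. The SAP already adds an interval for BCDVA that the protocol does not list. The downside is the sensitivity in Step 4 (0.033 logMAR against under 0.001 decimal for an assumed 5 of 90 eyes), which the last item makes visible.
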